•	To determine if there are any dose dependent changes in the absorption of GSK2982772 following single dose administration selected GSK2982772 MR prototype coated tablet formulations (Optional Part B)	•	GSK2982772 AUC(0-inf), AUC(0-t), AUC(0-24), $C_{max,}\ C_{24h}\ and\ T_{max}$
•	To assess the impact of a standard breakfast on the PK of GSK2982772 following single dose administration of one or more selected MR prototype coated tablet formulations (240 mg) (Part A - optional)	•	GSK2982772 AUC _(0-inf) , AUC _(0-t) , C_{max} , T_{max} and $t_{1/2}$, relative bioavailability (Frel _{FE}), relative bioavailability (Frel _{Formulation}), based on AUC and C_{max}
•	To assess the impact of a delayed meal on the PK of GSK2982772 following single dose administration of one or more selected MR prototype coated tablet formulations (240 mg) (Part A - optional)	•	GSK2982772 AUC _(0-inf) , AUC _(0-t) , C_{max} , T_{max} and $t_{1/2}$, relative bioavailability (Frel _{FE}), relative bioavailability (Frel _{Formulation}), based on AUC and C_{max}
•	To assess the impact of evening dosing (Optional Part B, Period 7 only) on the PK of GSK2982772 following single dose administration selected GSK2982772 MR prototype coated tablet formulations.	•	GSK2982772 AUC _(0-inf) , AUC _(0-t) , C_{max} , T_{max} and $t_{1/2}$, relative bioavailability (Frel (time effect), based on AUC and C_{max}

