units of the optimum MR formulation selected from Part A. If the in-vivo profile of either or both the 120 mg or 240 mg tablets (or alternative strengths) differs from the optimal profile with the 240 mg, the ratio of the polymers K3LV, K100LV and/or K4M may be adjusted within each of the alternative strengths. In order to assess the effect of the aperture on the in vivo performance of the formulation, a fully coated tablet (i.e., without apertures) may be assessed in Part B, Period 3 onwards. If fully coated tablet(s) are dosed, the core composition will match a previously dosed formulation to allow a valid comparison. To investigate whether the between-subject variability in absorption time observed following administration of 480 mg tablet with a high-fat breakfast (administered in previous periods) can be reduced; a change to the food regimen or time of administration may be explored in Part B, Period 7. Subjects may be dosed in the fasted state or fed state (standard or high-fat breakfast/evening meal) or in the fasted state followed by a delayed standard or high-fat breakfast/evening meal, on the morning or evening of Day 1. Prior to initiation of Part B, a substantial amendment to the investigational medicinal product dossier (IMPD), will be submitted to the MHRA for approval, to include updated information on the selected GSK2982772 MR prototype coated tablet formulations at alternative strengths.

As this is a Phase 1 study, the most relevant population is healthy participants which allows characterisation of safety, tolerability and PK in a homogenous population without potential biases from a patient population. The European Medicines Agency (EMA) recommends including participants aged 18 years and older with normal weight, who are non-smokers, without a history of alcohol or drug abuse. The latter criteria are proposed to avoid interaction on drug metabolism and to avoid non-compliance. Therefore, this study will enrol healthy male and female participants aged between 18 to 65 years of age.

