10.4. Statistical Analyses

10.4.1. Pharmacokinetic Analyses

All PK analyses will be performed on the PK Population.

For both parts of the study, plasma GSK2982772 concentration-time data will be analysed by non-compartmental methods.

The plasma concentration-time data for each of the regimens, the following PK parameters will be determined, as data permit:

- maximum observed plasma concentration (C_{max}).
- time to C_{max} (T_{max}).
- the elapsed time from dosing at which GSK2982772 was first quantifiable in a concentration vs time profile (T_{lag}).
- observed concentration at 24 hours post-dose (C_{24h}).
- observed concentration at 8 and 12 hours post-dose (C_{8h} and C_{12h}) for IR only.
- area under the plasma concentration vs time curve (AUC_(0-t), AUC₍₀₋₂₄₎ and AUC_(0-inf)).
- the percentage of AUC extrapolated beyond the last measured time point (AUC%extrap).
- terminal half-life $(t_{1/2})$.
- relative bioavailability (Frel_{formulation}) of test formulations (under fed or fasted conditions) vs reference formulation based on AUC₍₀₋₂₄₎ and AUC_(0-inf) (or AUC_(0-t) if AUC_(0-inf) can't be derived) and C_{max}.
- relative bioavailability (Frel_{FE}) of fed (high-fat breakfast or high-fat evening meal, standard breakfast or standard evening meal or delayed meal (30 or 60 minutes) vs fasted based on AUC and C_{max}.
- relative bioavailability (Frel(time effect) of evening dosing vs morning dosing based on AUC and C_{max})
- relative bioavailability (Frel_{MRFormulation}) of MR prototype coated tablet formulations relative to each other, as appropriate, based on AUC and C_{max} (optional Part B only)
- C_{max}/Dose and AUC/Dose (optional Part B only)

Descriptive statistics (n, arithmetic mean, standard deviation [SD], 95% CI, minimum, median and maximum) will be calculated by treatment for all PK concentrations over time and for the derived PK parameters. In addition, for log_e-transformed PK parameter variables geometric mean, 95% CI and %CV_b (100 * $\sqrt{(exp(SD2) - 1)}$) will be provided, where the SD is the standard deviation of log-transformed data.

Endpoint	Statistical Analysis Methods
Primary	The primary PK endpoints to compare MR formulations with IR formulations will be summarised descriptively. Ratios of $AUC_{(0-inf)}$, $AUC_{(0-24)}$, $(AUC_{(0-t)}$, if $AUC_{(0-inf)}$ cannot be derived), C_{max} , C_{24h} for MR formulation to IR formulation will be computed with 90% CI.

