•	To determine if there are any dose dependent changes in the absorption of GSK2982772 following single dose administration selected GSK2982772 MR prototype coated tablet formulations (Optional Part B)	•	GSK2982772 AUC(0-inf), AUC(0-t), AUC(0-24), Cmax, C24h and Tmax
•	To assess the impact of a standard breakfast on the PK of GSK2982772 following single dose administration of one or more selected MR prototype coated tablet formulations (240 mg) (Part A - optional)	•	GSK2982772 AUC(0-inf), AUC(0-t), Cmax, Tmax and t1/2, relative bioavailability (FrelFe), relative bioavailability (FrelFormulation), based on AUC and Cmax
•	To assess the impact of a delayed meal on the PK of GSK2982772 following single dose administration of one or more selected MR prototype coated tablet formulations (240 mg) (Part A - optional)	•	GSK2982772 AUC(0-inf), AUC(0-t), Cmax, Tmax and t1/2, relative bioavailability (FrelFe), relative bioavailability (FrelFormulation), based on AUC and Cmax

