5. CONSIDERATIONS FOR DATA ANALYSES AND DATA HANDLING CONVENTIONS

5.1. Study Treatment & Sub-group Display Descriptors

	Treatment Group Descriptions									
	RandAll NG	Data Displays for Re	porting							
Code	Description	Description	Order in TLF							
Part A										
Α	GSK2982772 240mg MR RR1 oral single dose	MR-12h 240mg Fasted	2							
В*	GSK2982772 240mg MR RR2 oral single dose	IR 240mg Fasted	1							
C*	GSK2982772 240mg IR oral single dose	MR-18h 240mg Fasted	3							
D	GSK2982772 240mg MR RR3 oral single dose	MR-18h 240mg Fed (High-Fat)	5							
E	GSK2982772 240mg MR RR4 oral single dose	MR-12h 240mg Fed (High-Fat)	4							
F	GSK2982772 240mg MR fed state	MR-16h 240mg Fasted	6							
Part B		 								
G	GSK2982772 120mg MR oral single dose	MR-16h 480mg Fasted	1							
Н	GSK2982772 480mg MR oral single dose	MR-16h 960mg Fasted	5							
J	GSK2982772 MR oral single dose 1	MR-16h 480mg Fed (High-Fat)	3							
K	GSK2982772 MR oral single dose 2	MR-16h 120mg Fasted	6							
L	GSK2982772 MR oral single dose 3	MR-16h 480mg Fed (High-Fat) (Enteric Coated)	4							
М	GSK2982772 MR oral single dose 4	MR-16h 480mg Fed (Standard)	2							

^{*} In Part A, the treatments for Period 2 and 3 were reversed in order due to availability of the drug at site. For Period 2 participants received "GSK2982772 240mg IR oral single dose" and Period 3 participants received "GSK2982772 240mg MR RR2 oral single dose".

Safety listings may be presented chronologically instead of in the order suggested above.

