- Exact non-parametric Hodges-Lehmann estimation of location shift will be fitted.

Model Results Presentation

 For each relative bioavailability, the median difference and 90% CI for median difference will be presented.

Part A - Formulation

Endpoint (AUC, C_{max}, C_{24h} in log scale)

- AUC_(0-inf)
- AUC_(0-t)
- AUC_(0-24h)
- C_{max}
- C_{24h}
- T_{max}

Relative Bioavailability

- MR-12h 240mg Fasted vs IR 240mg Fasted
- MR-18h 240mg Fasted vs IR 240mg Fasted

- MR-16h 240mg Fasted vs IR 240mg Fasted
- MR-18h 240mg Fed (High-Fat) vs MR-12h 240mg Fed (High-Fat)

Part A – Food Effect

Endpoint (AUC, Cmax in log scale)

- AUC_(0-inf)
- AUC_(0-t)
- C_{max}
- T_{max}

Relative Bioavailability

- MR-18h 240mg Fed (High-Fat) vs MR-18h 240mg Fasted
- MR-12h 240mg Fed (High-Fat) vs MR-12h 240mg Fasted

Part B – Dose Effect

Endpoint (AUC, C_{max}, C_{24h} in log scale)

- AUC_(0-inf)
- AUC_(0-t)
- AUC_(0-24h)
- C_{max}
- C_{24h}
- T_{max}

Relative Bioavailability

- MR-16h 960mg Fasted vs MR-16h 120mg Fasted
- MR-16h 480mg Fasted vs MR-16h 120mg Fasted
- MR-16h 960mg Fasted vs MR-16h 480mg Fasted

Part B – Food Effect

Endpoint (AUC, Cmax in log scale)

- AUC_(0-inf)
- AUC_(0-t)
- C_{max}
- T_{max}

Relative Bioavailability

• MR-16h 480mg Fed (High-Fat) vs MR-16h 480mg Fasted

Part B – Enteric Coating Effect

Endpoint (AUC, C_{max}, C_{24h} in log scale)

- AUC_(0-inf)
- AUC_(0-t)
- C_{max}
- C_{24h}
- T_{max}

Relative Bioavailability

• MR-16h 480mg Fed (High-Fat) (Enteric Coating) vs MR-16h 480mg Fed (High-Fat)

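### The 480 mg standard-meal regimen in Part B enters no SAP contrast, and no estimate compares the spread of absorption time between meals

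*Protocol*

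**What the plan says.** Protocol 5.4 states the aim for the last Part B period: "To investigate whether the between-subject variability in absorption time observed following administration of 480 mg tablet with a high-fat breakfast" can be lowered. It adds that "a change to the food regimen or time of administration may be explored in Part B, Period 7". The amendment summary at the front of the protocol gives the same reason.

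In Protocol 4, the only objective tied to that period is "To assess the impact of evening dosing (Optional Part B, Period 7 only) on the PK of GSK2982772". The standard-breakfast and delayed-meal objectives are confined to "selected MR prototype coated tablet formulations (240 mg) (Part A - optional"). Protocol 10.4.1 is broader. For AUC and Cmax, it defines the food-effect bioavailability ratio as "fed (high-fat breakfast or high-fat evening meal, standard breakfast or standard evening meal or delayed meal (30 or 60 minutes) vs fasted".

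SAP 5.1 lists six Part B regimens. Code M is the one whose display label begins "MR-16h 480mg Fed (Standard". The only Part B food contrast in SAP 8.1.5.1 is "MR-16h 480mg Fed (High-Fat) vs MR-16h 480mg Fasted". SAP 2.2 repeats the objective "To assess the impact of a standard breakfast on the PK of GSK2982772", again for Part A at 240 mg. SAP 2.1 declares no change to the planned analysis, citing the protocol dated 23 July 2018.

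For Tmax, SAP 8.1.5.1 plans a Hodges-Lehmann location shift. SAP 8.1.2 and Table 3.9 give SD, minimum, median and maximum of each derived parameter by dose and prandial state. SAP 8.1.1.2 includes Tmax and Tlag among those parameters.

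**The concern.** A regimen was listed for reporting, but the enumerated analysis does nothing with it beyond description. If the statistical output follows the list in SAP 8.1.5.1, the report will hold no named estimate or interval for standard meal against fasted or against high-fat at 480 mg. The second of these is the comparison that the rationale in Protocol 5.4 calls for when the meal is what changes.

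The rationale is also about spread, whereas every planned comparison is about level: ratios of geometric means, or a shift in Tmax. A reader would be left to set two SDs side by side, each from roughly 12 to 16 people, with nothing to show how uncertain their ratio is. That invites over-reading in either direction.

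**Working it through.** The plan states no figure on this point, so the check is an audit of the contrasts, followed by an illustration of how precise the added estimate would be.

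**1. Regimens against contrasts (SAP 5.1 and 8.1.5.1, Part B).**

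| Regimen (MR-16h) | Dose contrasts (3) | Food contrast (1) | Coating contrast (1) |
|---|---|---|---|
| G: 480 mg fasted | yes | yes | no |
| H: 960 mg fasted | yes | no | no |
| J: 480 mg high-fat | no | yes | yes |
| K: 120 mg fasted | yes | no | no |
| L: 480 mg high-fat, enteric coated | no | no | yes |
| M: 480 mg standard meal | no | no | no |

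There are 3 + 1 + 1 = 5 contrasts, and 0 of 5 include M. All six Part A regimens appear in at least one Part A contrast, so M is the only one of the 12 listed regimens that is never compared.

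**2. Displays (SAP 10.10.8.2).** The page lists of Figures 3.10 and 3.11 name the three fasted doses, then 480 mg fasted and high-fat, then high-fat with and without the alternative coating. Figure 3.14 names high-fat vs fasted only. None names the standard meal. Table 3.9 and Figure 3.9 are organised by dose and prandial state, so they do cover it.

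**3. Level or spread.** Log-scale AUC, Cmax and C24h yield geometric mean ratios, and Tmax yields a location shift. Two regimens can have the same median Tmax and very different spread, so neither method addresses the aim in Protocol 5.4. %CVb is produced only for log-transformed parameters, and SAP 8.1.1.2 excludes Tmax from log transformation. Tmax therefore has SD and range, but no %CVb and no comparison.

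**4. Precision of a paired SD ratio (illustration).** Inputs: n = 12 (minimum evaluable) and n = 16 (planned enrolment), from Protocol 5.2. Normality and the within-pair correlation r are assumptions that the documents do not give; r is taken as 0 to 0.5. With t the 95th percentile of the t distribution on n − 2 degrees of freedom, the normal-theory 90% interval is the observed ratio multiplied and divided by f, where

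K = 1 + 2(1 − r²)t²/(n − 2), and f = √(K + √(K² − 1)).

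| n | t | r | K | f | 1/f |
|---|---|---|---|---|---|
| 12 | 1.812 | 0 | 1.657 | 1.73 | 0.58 |
| 12 | 1.812 | 0.5 | 1.493 | 1.61 | 0.62 |
| 16 | 1.761 | 0 | 1.443 | 1.58 | 0.63 |
| 16 | 1.761 | 0.5 | 1.332 | 1.49 | 0.67 |

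The last column is the observed SD ratio below which the interval excludes 1. The observed SD would have to fall to about 0.58–0.62 of its high-fat value with 12 participants, or 0.63–0.67 with 16.

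**5. Why not use that formula for the analysis itself.** The modified-release schedule samples every 2 hours from 2 to 32 hours (Protocol Table 2), so Tmax is coarse and need not be normal. As a stress test, with equal SDs and an assumed lognormal shape (sigma 0.8), the one-sided 5% Pitman-Morgan test at n = 12 rejects about 21% of the time. The formula serves here only to show the order of magnitude.

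**The case against.** The strongest reply is that this is an exploratory study with no formal hypotheses, and the spread is already reported: Table 3.9 gives SD and range of Tmax and Tlag for both meals, and Figure 3.9 shows individual profiles. That stands. A reader might infer that the variability question goes wholly unanswered, and the documents do not support this. What is missing is an estimate of the comparison and its uncertainty.

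A second reply is that general text covers the food contrast. SAP 10.6.5 lists fed vs fasted without restricting the meal, SAP 8.1.5.1 promises estimates for each treatment period, and Tables 3.14 and 3.15 carry no restricting note. This softens the standard vs fasted gap. But none of these lines names the standard meal, the explicit list and Figure 3.14 name only high-fat, and fed vs fasted cannot yield standard vs high-fat.

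Three further readings are tempting and should be avoided:

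- That code M was Period 7, so participants took an extra dose for nothing. In the protocol, M is the seventh Part B regimen. The SAP has six codes with no I, and its schedule stops at Period 6. The link is an inference, and the gap is the same whichever period it was.
- That the standard-breakfast objective has been left without data by mistake. It is marked optional in Part A, and an option not used is not an error.
- That the rationale concerns only meals. It also covers dosing time, which has its own objective and a planned comparison in Protocol 10.4.1, though on level rather than spread.

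**Conclusion.** The point holds as an incomplete analysis list and a missing estimate. One of six Part B regimens appears in 0 of 5 contrasts and in none of Figures 3.10, 3.11 and 3.14, although the current Protocol 10.4.1 plans a standard-meal food-effect ratio. The no-change statement in SAP 2.1 does not flag the omission. It cites a protocol date earlier than the April 2019 amendment that added Period 7. These counts rest on the text alone.

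The aim in Protocol 5.4 has descriptive support only, with no interval for a comparison of spread. The precision figures depend on assumed normality and a correlation of 0 to 0.5, and on 12 to 16 people having taken both meals. With replacements or withdrawals the number of pairs could be smaller. No existing result becomes invalid. This is an inexpensive improvement that lets the report speak to its own stated purpose.

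**What to change.** 1. In SAP 8.1.5.1, Part B food effect, add the 480 mg standard-meal regimen vs 480 mg fasted and vs 480 mg high-fat, for the endpoints already listed there: AUC(0-inf), AUC(0-t), Cmax and Tmax.
2. Add the regimen to the page lists of Figures 3.10 and 3.11, and both contrasts to Figure 3.14. Carry them into Tables 3.14 and 3.15.
3. As exploratory, add the ratio of between-subject SDs of Tmax, standard over high-fat, in participants who took both. Give a 90% interval from a bootstrap that resamples participants, not a normal-theory Pitman-Morgan interval by default. Do the same for Tlag. If nearly everyone shares one Tlag value on the sampling grid, report the range instead, because the ratio would be unstable. SD of log Cmax is not a substitute, since it does not measure absorption time.
4. State in the SAP that Tmax and Tlag stand for absorption time in this comparison, and in the report that only a large reduction could be shown with this many participants. A bootstrap interval is itself approximate at this size.
5. State in SAP 5.1 the period in which each regimen was given, and update SAP 2.1 to refer to the current protocol.

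The mixed model has a formulation term for each study part, so the added AUC and Cmax ratios are further contrasts from that model. The Tmax shifts and SD ratios are separate short calculations. The cost is SAP wording and a few table rows and figure entries, with no new data and no change to dosing or conduct. The one drawback is the wide interval, which is itself worth showing.

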5.5. Dose Justification

In the blinded high dose PK study (205184) in healthy participants, single doses up to 720 mg/day appear to be well-tolerated with no safety concerns identified. No SAEs or deaths have been reported. Repeat dosing with up to 720 mg/day x 14 days is ongoing.

Single doses are to be used in this study since single doses are generally more sensitive than steady-state dosing in assessing rate and extent of release of the drug substance from the drug product into the systemic circulation. In addition, GSK 2982772 has time independent pharmacokinetics as demonstrated with similar single and repeat dose PK profiles following 14 days dosing with GSK2992772 Immediate Release (Study 200975) and following 3 days dose with minitab MR (Study 205017). Single doses are also required for development of in-vitro / in-vivo correlation which may be developed for the DiffCore formulation at a later date".

In Part A, a dose of 240 mg has been selected as this is expected to be safe and well tolerated, and is within the expected dose range that is planned to be taken forward into the Phase 2b dose ranging studies.

In Part B, the selection of the doses will be based on the results from Part A. The highest dose will not be predicted to exceed the GSK2982772 systemic exposure associated with the single day administration of 240 mg TID (i.e., mean AUC₍₀₋₂₄₎ of 45.0 μ g.h/mL and

mean C_{max} of 4.3 µg/mL). These exposures are below those achieved at the monkey and rat no observed adverse effect levels in the 13-week toxicology studies.

6. STUDY POPULATION

Prospective approval of protocol deviations to recruitment and enrolment criteria, also known as protocol waivers or exemptions, is not permitted.

Quotient Sciences must have a full medical history from each participant's general practitioner within the last 12 months, prior to enrolment in the study. Participants will be recruited from the Quotient Sciences panel or by direct advertising to the public.

Before participants are admitted to the clinic, The Over Volunteering Prevention System will be checked to ensure that each participant has not participated in a study at another site within at least 3 months of the dosing date.

6.1. Inclusion Criteria

Participants are eligible to be included in the study only if all of the following criteria apply:

Age

1. Participant must be 18 to 65 years of age inclusive, at the time of signing the informed consent.

Type of Participant and Disease Characteristics

2. Participants who are overtly healthy as determined by medical evaluation including medical history, physical examination, laboratory tests, and cardiac monitoring.

Weight

3. Body weight \geq 50 kg and body mass index within the range 19.0 to 32.0 kg/m² (inclusive).

Sex

- 4. Male or female
- a. Male Participants:

Male participants are eligible to participate if they agree to the following during the intervention period until completion of the final follow up visit after the last dose of study treatment:

• Refrain from donating sperm

Plus either:

• Be abstinent from heterosexual or homosexual intercourse as their preferred and usual lifestyle (abstinent on a long term and persistent basis) and agree to remain abstinent

OR

- Must agree to use contraception/barrier as detailed below
 - Agree to use a male condom and should also be advised of the benefit for a female partner to use a highly effective method of contraception as a condom may break or leak when having sexual intercourse with a woman of childbearing potential who is not currently pregnant
 - Agree to use male condom when engaging in any activity that allows for passage of ejaculate to another person.
- b. Female Participants:
 - A female participant is eligible to participate if she is not pregnant or breastfeeding, and at least one of the following conditions applies:
 - Is not a woman of childbearing potential (WOCBP)

OR

- Is a WOCBP and using a contraceptive method that is highly effective (with a failure rate of <1% per year), preferably with low user dependency, as described in Appendix 5 for at least 30 days before first dose until completion of the final follow up visit after the last dose of study treatment and agrees not to donate eggs (ova, oocytes) for the purpose of reproduction from Day 1 until 3 months after the last dose. The investigator should evaluate the effectiveness of the contraceptive method in relationship to the first dose of study intervention.
- A WOCBP must have a negative highly sensitive serum pregnancy test within 24 hours before the first dose of study intervention.
- Additional requirements for pregnancy testing during and after study intervention are located in Appendix 5.
- The investigator is responsible for review of medical history, menstrual history, and recent sexual activity to decrease the risk for inclusion of a woman with an early undetected pregnancy

Informed Consent

5. Capable of giving signed informed consent as described in Appendix 3 which includes compliance with the requirements and restrictions listed in the ICF and in this protocol.

